### **Protocol History**

**Original version:** 25May2016 (Approved by FDA 5/27/2016)

**Amendment 1:** 20Sept2016

**Amendment 2:** 27Sept2017

**Amendment 3:** 26Jan2018

**Amendment 4:** 04Jan2019

**Amendment 5:** 29Jan2019

**Amendment 6:** 25Apr2019

**Amendment 7:** 28Aug2020

**Amendment 8:** 11Oct2021

**Amendment 9:** 26Jul2022

**Amendment 10:** 14Nov2022

## 1 TRIAL SUMMARY

Abbreviated Title	Pembrolizumab and Poly-ICLC in MRP colon cancer
Trial Phase	1/2
Clinical Indication	Phase 1: All solid tumors; Phase 2: Metastatic Mismatch Repair Proficient (MRP) Colon Cancer, which includes disease that is microsatellite instability status low (MSI-low) and microsatellite stable (MSS).
Trial Type	Interventional
Type of control	Historical
Route of administration	Pembrolizumab IV, Poly-ICLC IM
Trial Blinding	None
Treatment Groups	1
Number of trial subjects	31
Estimated enrollment period	18 months
Estimated duration of trial	30 months
Duration of Participation	2-3 years
Estimated average length of treatment per patient	6 months

## 2 TRIAL DESIGN

### 2.1 Trial Design

This study will enroll its patients into two separate phases:

#### 1) Run In phase

[figure not shown]
- a. Aimed to determine if poly-ICLC can be safely combined with standard dosages of pembrolizumab.
  - i. Poly-ICLC will be administered intramuscularly twice weekly at two dose levels: 1 mg or 2 mg
  - ii. Pembrolizumab will be administered 200 mg IV q3w
- b. Each dose level enrolls 3-6 patients, with the potential for 12 patients if dose limiting toxicity (DLT) occurs at each dosing level.
- c. Patients with any solid tumor that is unresponsive to at least one line of therapy are eligible for the dose escalation phase unless curative options exist

#### 2) Phase II trial expansion

[figure not shown]
- a. The combination will then be administered at the recommended phase II dose in up to 27 patients with metastatic MRP colon cancer

### 2.2 Trial Diagrams

### 2.2.1 Trial Phases

### 2.2.2 Trial Treatments

### 3 OBJECTIVES & HYPOTHESES

#### 3.1 Primary Objectives & Hypotheses

##### 3.1.1 Objectives:

- a. Phase 1: Determine the maximum tolerated dose of poly-ICLC that can be combined with pembrolizumab
- b. Determine the response rate, as assessed by RECIST 1.1, of metastatic MRP colon cancer that has progressed following two lines of therapy in the metastatic setting to the combination of pembrolizumab and poly-ICLC

##### 3.1.2 Hypotheses:

- a. Poly-ICLC will generate an inflammatory response increasing epitope recognition and development of tumor reactive T cells at the tumor site. However, interferon alpha and gamma produced by the poly-ICLC will increase PD-L1 expression and limit new T cell development. Thus, PD1 blockade will increase the effectiveness of the therapy.
- b. Phase 1 – Combination of Poly-ICLC and Pembrolizumab is tolerable at the doses proposed for this intervention
- c. Phase 2 – Combination of poly-ICLC and pembrolizumab has increased efficacy compared to pembrolizumab alone in patients with colon cancer. The RR will increase to 20% for the combination treatment from an expected 5% response rate for pembrolizumab alone.

#### 3.2 Secondary Objectives

- a. Phase I and II - Determine the adverse event profile and dose limiting toxicities of the combination of pembrolizumab and poly-ICLC
- b. Determine the progression free survival rate, overall survival rate and duration of response of recurrent metastatic MRP colon cancer to the combination of pembrolizumab and poly-ICLC

#### 3.3 Exploratory Objectives

- a. Evaluation of inflammatory state in tumor biopsies with specific attention to definition of tumor infiltration with hematopoietic cells, cell surface signaling molecule expression
- b. Evaluation of pre-treatment and post-treatment microarray panels in tumor samples and peripheral blood
- c. Determine response rate by irRECIST

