### 8.3 Study Design/Endpoints

Phase I: Classical 3+3 design will be employed and will include dose-escalation to determine the RP2D of Poly-ICLC to be combined with pembrolizumab. We will consider two dose levels, 1 and 2 mg of Poly-ICLC.

Phase II: Primary endpoint is the response rate defined according to RECIST 1.1 criteria. irRECIST response will be assessed as an exploratory endpoint.

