### 11.3 Immune Related Response Criteria (irRC) with Response Evaluation Criteria in Solid Tumors (RECIST) 1.1

Responses will be evaluated in all subjects. Because of direct clinical observations of immune cell influx into tumor causing enlargement in some patients prior to sustained response, recently it has been suggested that clinical trials involving the use of immunotherapy use alternative guidelines, called immune related response criteria (irRC) to determine radiographic response or progression after therapy. The criteria for evaluation of response are those defined in Wolchok JD, Hoos A, O'Day S, et al. Guidelines for the evaluation of immune therapy activity in solid tumors: Immune-related response criteria. Clin Cancer Res 2009; 15:7412-7420.

These recommendations have been used in recent clinical trials. One study of 227 subjects with metastatic melanoma showed that the approximately 10% of patients who had PD by modified WHO criteria but either CR, PR or SD by irRC had a similar overall survival as those patients who had SD, PR or CR by both criteria. The irRC was created using bidimensional measurements (as previously widely used in the WHO criteria). We have taken the concepts of the irRC and combined them with the recently revised RECIST 1.1 to come up with the modified irRC used in this protocol. Consistent with the irRC, the main changes from RECIST 1.1 are (a) a requirement for confirmation of both progression and response by imagining at least 4 weeks

after initial imaging and (b) not automatically calling the appearance of new lesions progressive disease if the total measurable tumor burden has not met criteria for progressive disease.

For immune-related response criteria (irRC), only index and measurable new lesions are taken into account. At baseline tumor assessment on this trial, target lesions will be measured along the longest axis and the measurements will be summed, called sum of largest diameter (SLD). These lesions must be a minimum of 10mm per lesion, maximum of 5 target lesions, maximum of 2 per organ system. At each subsequent tumor assessment, the unidimensional measurement of target lesions and of new measurable lesions are added together to provide the total tumor burden: As per the modified definitions below, all responses and progression except stable disease (SD) required confirmation on a consecutive scan at least 4 weeks from the initial observation).

Definitions of irRC:

Response	irRC

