New measurable lesions	Incorporated into tumor burden
New non-measurable lesions	Do not define progression (but precludes irCR)
Non-index lesions	Contributes to defining irCR (complete disappearance required)
Overall irCR	100% disappearance of all lesions, whether measurable or not, and no new lesions, in two consecutive observations not less than 4 wks from the date first documented. All measurable lymph nodes also must have reduction in short axis to <10mm.
Overall irPR	≥ 30% decrease in SLD compared with baseline confirmed by a consecutive assessment at least 4 wk after first documentation
Overall irSD	Not meeting criteria for irCR or irPR, in absence of irPD: 30% decrease in SLD compared with baseline cannot be established nor 20% increase compared with nadir.
Overall irPD	At least 20% increase in SLD compared with nadir (minimum recorded tumor burden) and an increase of at least 5mm over the nadir, confirmed by a repeat, consecutive observation at least 4 wk from the date first documented.

Overall responses derived from changes in index, non-index and new lesions as demonstrated in the following table:

Measurable response	Non-measurable response		Overall response using irRC
Index and new, measurable lesions (tumor burden)* %	Non-index lesions	New, non-measurable lesions	
Decrease 100%	Absent	Absent	irCR&
Decrease 100%	Stable	Any	irPR&
Decrease 100%	Unequivocal progression	Any	irPR&
Decrease $\geq$ 30%	Absent / Stable	Any	irPR&
Decrease $\geq$ 30%	Unequivocal progression	Any	irPR&
Decrease < 30% to increase < 20%	Absent / Stable	Any	irSD
Decrease < 30% to increase < 20%	Unequivocal progression	Any	irSD
Decrease $\geq$ 20%	Any	Any	irPD

\* Decreases assessed relative to baseline

& Assuming response (irCR) and progression (irPD) are confirmed by a second, consecutive assessment at least 4 weeks apart.

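### The overall-response matrix in Appendix 11.3 assigns irPD to a decrease of 20% or more, contradicting the appendix's own irPD definition (minor: one word, a footnote and a tie-break rule to correct)

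*Combined protocol and SAP*

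**What the plan says.** Section 3.3(c) lists "Determine response rate by irRECIST" as an exploratory objective, and section 8.3 repeats that "irRECIST response will be assessed as an exploratory endpoint". The immune-related rules are in Appendix 11.3, whose authors write: "We have taken the concepts of the irRC and combined them with the recently revised RECIST 1.1 to come up with the modified irRC". No other immune-related criteria appear in the document.

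Appendix 11.3 contains two tables.

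- **Definitions table.** Overall irPD is "At least 20% increase in SLD compared with nadir (minimum recorded tumor burden) and an increase of at least 5mm over the nadir", confirmed at least 4 weeks later. irPR is a confirmed fall of at least 30% from baseline. irSD is the remainder, and it too uses a 20% rise from nadir as its upper limit.
- **Overall-response matrix.** It is introduced with: "Overall responses derived from changes in index, non-index and new lesions as demonstrated in the following table". The irSD rows cover "Decrease < 30% to increase < 20" per cent. The last row, which is the only irPD row, is worded as a decrease of 20% or more, with any non-index and any new-lesion status. The footnote on reference points says only: "Decreases assessed relative to baseline".

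**The concern.** The matrix is presented as the rule that turns lesion changes into an overall call, and the direction of its progression threshold is reversed. Followed row by row, it attaches a progression call to patients whose tumours shrink and offers no call for patients whose tumours grow by 20% or more. Someone who programs or fills in overall response from the matrix, without returning to the definitions, would meet contradictory or missing calls for a named endpoint.

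Two smaller gaps sit beside the wrong word. The footnote gives no reference point for increases, whereas the definition uses nadir with a 5 mm minimum. The appendix also does not say which call applies when the response and progression thresholds are both met.

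**Working it through.** The plan gives no figure on this point, and no sample-size or power figure is involved. The check is whether the matrix gives one call, and only one, for each possible change in tumour burden.

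**Inputs (Appendix 11.3 matrix).** Decrease of 100%: irCR or irPR, depending on the other lesions. Decrease of 30% or more (taken here as short of 100%): irPR. Decrease under 30% to increase under 20%: irSD. Decrease of 20% or more: irPD.

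**Step 1: the matrix as printed.** Take each whole-percent change from -100% to +100%, which is 201 values.

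| Change in tumour burden | Number of values | Rows met as printed | Rows met if the last row reads as an increase |
|---|---|---|---|
| -100% to -30% | 71 | irCR or irPR, and irPD | irCR or irPR |
| -29% to -20% | 10 | irSD and irPD | irSD |
| -19% to +19% | 39 | irSD | irSD |
| +20% to +100% | 81 | none | irPD |

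Check: 71 + 10 + 39 + 81 = 201. As printed, 71 + 10 = 81 values meet two rows, 81 meet none and 39 meet exactly one. All 71 values in the response range also meet the irPD row. These are counts of grid points and say nothing about how many patients fall in each band. Growth under 20% does have a row, irSD.

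**Step 2: the last row read as an increase.** All 201 values then meet exactly one row, and none of the 71 response values meets irPD. This supports reading the row as a wording error: the irSD rows stop just below a 20% increase, and the reversed row leaves the space above them empty.

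**Step 3: two reference points.** Steps 1 and 2 use a single percent change. The definitions use two: baseline for response and nadir for progression. Take sums of 100 mm at baseline, then 50 mm, then 65 mm.

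- From baseline: (65 - 100) / 100 = -35%, which meets the irPR threshold.
- From nadir: (65 - 50) / 50 = +30%, a rise of 15 mm, which meets the irPD threshold and its 5 mm minimum.

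Both calls apply at the third scan even after the word is corrected. The irSD definition excludes irPD, but the irPR definition does not, so the text does not settle the matter. It can affect the response count: irPR needs confirmation on a consecutive scan, and 65 mm is still below 70 mm (100 x 0.70). The third scan would confirm the response if irPR prevails and would not if irPD prevails.

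**The case against.** The strongest answer is that the appendix corrects itself. The irPD definition, the irSD definition and the upper end of the irSD rows all point to an increase; one word disagrees. Responders and progressors can both be classified from the definitions, so the endpoint can still be derived. This stands, and it is why the point is minor.

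The endpoint is also exploratory under sections 3.3(c) and 8.3. The RECIST 1.1 response rate is primary in sections 3.1.1, 8.2.1 and 8.3 and is scored under Appendix 11.4, where progression is a 20% increase. That stands too. Section 4.2.3, however, calls the immune RECIST response rate primary. This is a separate conflict that needs its own reconciliation, and while it remains the matrix error cannot be set aside as bearing only on an exploratory endpoint.

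Two further reservations are fair. Section 3.3(c) says irRECIST while Appendix 11.3 says modified irRC, and the document never equates them; the link is an inference, though nothing else is available to score from. The word might also be a text-extraction error. The row is complete, with all four cells intact, so nothing in the text suggests one, but the source table should be looked at first. The footnote and tie-break gaps do not depend on that word.

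A reader might infer that the immune-related response rate would fall to zero because every responder is also called progressing. The documents do not support this. Nothing gives the irPD row precedence over the irCR and irPR rows. No immune-related response rate is assumed anywhere, since the 20% in section 8.4 sizes Phase II, whose endpoint in section 8.3 is RECIST 1.1. Nor does the plan include a comparison of the two response rates that could be distorted.

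**Conclusion.** The last row of the matrix in Appendix 11.3 is wrong as written, because it reverses the progression threshold that the same appendix defines. Read literally, every decrease of 20% or more carries an additional irPD call and growth of 20% or more has no call. The definitions table shows that this is a wording error and still allows correct scoring.

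The effect is limited to the immune-related response endpoint; the RECIST 1.1 response rate and the Phase II sample size are untouched. No effect in patients can be put on it from the documents. The conclusion rests on two assumptions: that Appendix 11.3 is what irRECIST refers to, and that the row was read correctly from the source. Severity: minor.

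**What to change.** In Appendix 11.3:

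1. Make the last matrix row match the document's own definition: *Increase ≥ 20% from nadir and at least 5 mm | Any | Any | irPD*.
2. Extend the footnote to: *Decreases assessed relative to baseline, increases relative to nadir*.
3. Add one sentence saying which call applies when a sum is both at least 30% below baseline and at least 20% above nadir, with the 100, 50, 65 mm sequence as a worked case.

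It would help to state in the same amendment that irRECIST in sections 3.3(c) and 8.3 means the modified irRC of Appendix 11.3. The conflict between section 4.2.3 and sections 3.1.1, 8.2.1 and 8.3 over the primary endpoint should be reconciled separately.

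The cost is a table row, a footnote and a sentence or two. No new data, visits or change in sample size are needed.

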### 4 BACKGROUND & RATIONALE

#### 4.1 Background

Refer to the Investigator's Brochure (IB)/approved labeling for detailed background information on Pembrolizumab (MK-3475). Refer to the Investigator's Brochure (IB) for detailed background information on Poly-ICLC

#### 4.1.1 Pharmaceutical and Therapeutic Background for pembrolizumab

The importance of intact immune surveillance in controlling outgrowth of neoplastic transformation has been known for decades. Accumulating evidence shows a correlation between tumor-infiltrating lymphocytes (TILs) in cancer tissue and favorable prognosis in various malignancies. In particular, the presence of CD8+ T-cells and the ratio of CD8+ effector T-cells / FoxP3+ regulatory T-cells seems to correlate with improved prognosis and long-term survival in many solid tumors.

The PD-1 receptor-ligand interaction is a major pathway hijacked by tumors to suppress immune control. The normal function of PD-1, expressed on the cell surface of activated T-cells under healthy conditions, is to down-modulate unwanted or excessive immune responses, including autoimmune reactions. PD-1 (encoded by the gene *Pdcd1*) is an Ig superfamily member related to CD28 and CTLA-4 which has been shown to negatively regulate antigen receptor signaling upon engagement of its ligands (PD-L1 and/or PD-L2). The structure of murine PD-1 has been resolved. PD-1 and family members are type I transmembrane glycoproteins containing an Ig Variable-type (V-type) domain responsible for ligand binding and a cytoplasmic tail which is responsible for the binding of signaling molecules. The cytoplasmic tail of PD-1 contains 2 tyrosine-based signaling motifs, an immunoreceptor tyrosine-based inhibition motif (ITIM) and an immunoreceptor tyrosine-based switch motif (ITSM). Following T-cell stimulation, PD-1 recruits the tyrosine phosphatases SHP-1 and SHP-2 to the ITSM motif within its cytoplasmic tail, leading to the dephosphorylation of effector molecules such as CD3 $\zeta$ , PKC $\theta$  and ZAP70 which are involved in the CD3 T-cell signaling cascade. The mechanism by which PD-1 down modulates T-cell responses is similar to, but distinct from that of CTLA-4 as both molecules regulate an overlapping set of signaling proteins. PD-1 was shown to be expressed on activated lymphocytes including peripheral CD4+ and CD8+ T-cells, B-cells, Tregs and Natural Killer cells. Expression has also been shown during thymic development on CD4-CD8- (double negative) T-cells as well as subsets of macrophages and dendritic cells. The ligands for PD-1 (PD-L1 and PD-L2) are constitutively expressed or can be induced in a variety of cell types, including non-hematopoietic tissues as well as in various tumors. Both ligands are type I transmembrane receptors containing both IgV- and IgC-like domains in the extracellular region and contain short cytoplasmic regions with no known signaling motifs. Binding of either PD-1 ligand to PD-1 inhibits T-cell activation triggered through the T-cell receptor. PD-L1 is expressed at low levels on various non-hematopoietic tissues, most notably on vascular endothelium, whereas PD-L2 protein is only detectably expressed on antigen-presenting cells found in lymphoid tissue or chronic inflammatory environments. PD-L2 is thought to control immune T-cell activation in lymphoid organs, whereas PD-L1 serves to dampen unwarranted T-cell function in peripheral tissues. Although healthy organs express little (if any) PD-L1, a variety of cancers were demonstrated to express abundant levels of this T-cell inhibitor. PD-1 has been suggested to regulate tumor-specific T-cell expansion in subjects with melanoma (MEL). This suggests that the PD-1/PD-L1 pathway plays a critical role in tumor immune evasion and should be considered as an attractive target for therapeutic intervention.

Pembrolizumab is a potent and highly selective humanized monoclonal antibody (mAb) of the IgG4/kappa isotype designed to directly block the interaction between PD-1 and its ligands, PD-L1 and PD-L2. KeytrudaTM (pembrolizumab) has recently been approved in the United States for the treatment of patients with unresectable or metastatic melanoma and disease progression following ipilimumab and, if BRAF V600 mutation positive, a BRAF inhibitor.

#### 4.1.2 Pharmaceutical and Therapeutic Background for poly-ICLC

Polyinosinic-Polycytidylic acid stabilized with poly-L-lysine and carboxymethylcellulose (Poly-ICLC, Hiltonol®) is a synthetic double-stranded ribonucleic acid (dsRNA) ‘host-targeted’ therapeutic viral-mimic and Pathogen-associated molecular pattern (PAMP) with broad innate and adaptive immune enhancing, vaccine adjuvant, antiviral and anti-proliferative effects. These effects are mediated partly by its induction of a ‘natural mix’ of interferons (IFNs), cytokines, and chemokines, activation of natural killer [NK] cells, myeloid dendritic cells via TLR3 and MDA5, T4 and T8 cells, and activation of several nuclear and cytoplasmic enzyme systems, including the oligoadenylate synthetase [OAS], the dsRNA dependent protein kinase [PKR], RIG-I Helicase, and MDA5 that are involved in antiviral and antitumor host defenses. It has been shown to have broad gene regulatory actions as well.

Poly-ICLC was used intravenously as an IFN inducer some years ago in patients with various types of cancers, including leukemia, lymphoma, gliomas, myeloma, juvenile laryngeal papillomatosis, renal cell carcinoma, breast cancer, ovarian cancer, and melanoma. In most of these early trials, about 6 mg/m^2 Poly-ICLC was generally used intravenously. Few objective responses were reported in these high dose clinical trials and Poly-ICLC was generally abandoned when recombinant IFN became available. It was subsequently determined that lower doses (10 to 50 µg/kg) of Poly-ICLC resulted in a broader host defense stimulation, a potent adjuvant and antiviral effects. Consequently, Poly-ICLC is currently being developed for use only at doses up to about 30 µg/kg and the data presented in the following sections focus on studies using Poly-ICLC in this target dose range.

#### **Pharmacokinetics and Product Metabolism in Humans**

Poly-ICLC is not detectable in serum 24 hours after administration. However, the clinical half-life of the OAS response to 30 µg/kg IM Poly-ICLC in healthy human volunteers is about 2.5 days, suggesting an optimum dose schedule of two or three times per week. Twenty-four of 29 patients treated with 10 to 20 µg/kg Poly-ICLC by IM injection showed at least a 300% increase in serum OAS. A significant association of serum OAS with tumor response has been observed in patients with malignant glioma participating in an open pilot trial.

#### **Mechanism of Action**

Poly-ICLC stimulates at least 4 interrelated systems, any of which (alone or in combination) might be responsible for its possible antitumor and antiviral activity; induction of IFN and multiple other cytokines, chemokines and costimulatory factors, a broad immune-enhancing effect, direct antiviral/antineoplastic effect, and modulation of gene expression.

Poly-ICLC induces a ‘natural mix’ of interferons, cytokines and chemokines, including IFN production. As expected, the amount of these measurable in serum is dose-dependent, although biologically significant induction likely occurs locally. In previous studies, the minimal serum IFN levels induced by the currently recommended low doses of Poly-ICLC have not been associated with antitumor or antiviral action. A study of the immunomodulatory effect of Poly-ICLC in cancer patients showed no detectable serum IFN in patients receiving 1 mg/m^2 poly-ICLC by IM injection. In contrast, IFN was detectable in the serum of patients receiving 4 mg/m^2 IV poly-ICLC.

Low-dose Poly-ICLC directly stimulates the immune system through activation of NK cells, myeloid dendritic cells via TLR3 and MDA5, T-cells, macrophages and by inducing a ‘natural mix of interferons, cytokines and chemokines’. Some of these actions are related to the potent PAMP-adjuvant actions of poly-ICLC with various vaccine platforms, as well as to the broad antiviral state induced by the drug.

The third action of poly-ICLC is a more direct broad host-targeted antiviral and perhaps antineoplastic effect mediated by the two IFN-inducible nuclear enzyme systems, the 2'5'-oligoadenylate synthase (OAS) and the double stranded RNA kinase P1/eIF2a kinase, also known as the PKR, as well as RIG-I helicase and MDA5. The concentration of the 2'5'-OAS was elevated in the peripheral blood mononuclear cells of all Poly-ICLC-treated patients. Intramuscular administration of low-dose Poly-ICLC increased NK cells and growth inhibitory activities and 2'5'-OAS levels to a greater extent than high-dose IV infusion. Clinically, a maximal OAS response was observed at an IM dose of 30 µg/kg Poly-ICLC, and was greatly decreased at greater than 100 µg/kg in normal volunteers. The hypothesis that OAS and/or PKR may be involved in the antineoplastic effect of Poly-ICLC may thus explain the relative ineffectiveness of high dose Poly-ICLC in early cancer trials. However, further studies are needed to confirm this.

A fourth aspect of the action of Poly-ICLC involves modulation of the expression of a broad range of innate immune and other genes in a pattern closely paralleling that of a live virus vaccine (YF). Some of these genes play critical roles in the body’s natural defenses against a variety of neoplasms and microbial infections, and in controlling other cell functions, including protein synthesis, programmed (apoptotic) cell death, cell metabolism, cellular growth, the cytoskeleton and the extracellular matrix.

